1 PROTOCOL SUMMARY

1.1 SYNOPSIS

Title:	A Prospective, Multicenter, Randomized, Double-Blind, Phase 3 Study to Evaluate the Safety and Efficacy of a Gel Formulation of Esmolol Hydrochloride (Galnobax®) in Treating Diabetic Foot Ulcers
Study Description:	The purpose of the current Study is to determine the safety and effectiveness of Galnobax® plus Standard of Care versus only Standard of Care, in treating DFU. In addition, Study is designed to investigate the safety of Galnobax® vehicle for establishing non-deleterious effects of Vehicle on wound healing in the Subjects with DFU.
Objectives:	The objective of this Study is to evaluate efficacy and safety of Galnobax® gel (14% twice daily application) plus Standard of Care treatment versus only Standard of Care for healing of DFU.
	Primary Objective: 
1. To assess the efficacy of Galnobax® in terms of proportion of Subjects achieving Target Ulcer Closure within 12-week Treatment Phase upon application of Galnobax® plus Standard of Care as against only Standard of Care treatment, as assessed by the blinded Investigator.
	Secondary Objectives: 
1. To compare Time to Target Ulcer Closure within the 12-week Treatment Phase, upon application of Galnobax® plus Standard of Care as against only Standard of Care treatment, as assessed by the blinded Investigator.2. To compare proportion of Subjects achieving Target Ulcer Closure till End of Study upon application of Galnobax® plus Standard of Care as against only Standard of Care treatment, as assessed by the blinded Investigator.

	
Safety Objectives:
 
 1. To investigate the safety of Galnobax® treatment during the Study. 2. To investigate the safety of Galnobax® vehicle for establishing non-deleterious effects of Vehicle on wound healing.

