Endpoints:	
Primary Endpoint:
 
Efficacy endpoint: The efficacy assessment will involve Galnobax® plus Standard of Care and only Standard of Care groups
 
 1. Proportion of Subjects achieving Target Ulcer Closure within 12-week Treatment Phase, as assessed by blinded Investigator. 
Secondary Endpoints:
 
Efficacy endpoints:
 
 1. Time to Target Ulcer Closure during the 12-week Treatment Phase, as assessed by the blinded Investigator. 2. Proportion of Subjects achieving Target Ulcer Closure till End of Study, as assessed by the blinded Investigator. 
Safety endpoints:
 
 1. Proportion of Subjects with treatment emergent adverse events (TEAEs). 2. Proportion of Subjects with events related to the local wound assessment of Target Ulcer in Vehicle plus Standard of Care group.
Study Population:	
A maximum of 350 Subjects will be randomized for this Phase 3 clinical Study who have DFU and satisfy eligibility criteria given below and in Section 5. The break-up of these 350 Subjects is as follows:
 
Group 1: Galnobax® + SoC such that minimum number of Subjects in this group is 120.
 
Group 2: SoC alone such that minimum number of Subjects in this group is 120.
 
Provision for drop-outs in Groups 1 and 2: 20% i.e. 60 Subjects
 
Group 3: Vehicle + SoC such that the maximum number of Subjects in this group is 50 to evaluate the safety of Galnobax® vehicle.
 
Eligibility Criteria
 
a. Inclusion criteria
 
The Subjects who satisfy all the following inclusion criteria will be enrolled in the Study and subsequently randomized:

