Additionally, the non-clinical PK studies evidence that by application of Galnobax®, Esmolol hydrochloride is minimally absorbed (less than 10 ng/mL in rats and average maximum concentration of 30 ng/mL in minipigs) into systemic circulation, thereby evidencing that Galnobax® is safe to use in the treatment of DFU. The above observations and the fact that Esmolol hydrochloride is a pharmaceutically approved drug with well elucidated safety profile, suggest that Galnobax® has significantly favorable risk/benefit profile.²¹

Clinical Studies

The efficacy analysis of Phase 1/2 clinical Study of Galnobax® numerically establishes that Galnobax® 14% treatment has advantage in terms of area and volume reduction over the Vehicle and Galnobax® 20%. This advantage of Galnobax® 14% is more pronounced in hard to heal DFU:

- **In plantar DFU:** Galnobax® 14% showed 98.1% area closure Vs 75.8% for Placebo. The median time for complete wound closure was 35 days for Galnobax® 14% Vs 64 days for Placebo²¹
- **In older DFU:** On DFUs older than 8 weeks at baseline, Galnobax® 14% group showed complete closure in 75% Subjects Vs 43% in Placebo group²¹

The safety analysis of Phase 1/2 clinical Study establishes and reconfirms the findings of the non-clinical studies that Galnobax® is safe for long term use (tested for 12-weeks) in both 14% and 20% concentrations. Overall 29 adverse events (AEs) were observed in the Study and only two were related to the Study treatment. These two AEs were local mild allergic reactions which were found to be reversible. The safety of Galnobax® is further reinforced by the pharmacokinetic analysis of Phase 1/2 clinical Study which establishes that the systemic concentration of its drug substance (Esmolol hydrochloride) was below quantification limit (10 ng/mL) at any time during the

treatment period, irrespective of wounds of different sizes and doses of Galnobax®. This observation is significantly lower than:

- Systemic concentration of 868-1470 ng/mL observed for approved doses of intravenous Esmolol hydrochloride
- Human peak plasma concentration of 500, 1200 and 2500 ng/mL respectively observed for the infusion of Esmolol hydrochloride at the rate of 100, 250 and 500 µg/kg/min²²

Considering the above facts, it is proposed to investigate Galnobax® 14% in a Phase 3 Study to establish safety and efficacy with statistical significance.

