2.3.2 KNOWN POTENTIAL BENEFITS

Basic science and translational investigation are intensively researching the key abnormalities responsible for altering the wound-healing process in DM.²⁴ Yet, in spite of some available therapies, DFU still remains ineffectively treated in 67% of the cases resulting in lower extremity

amputations in about 15% of the cases.²⁵ Thus, DFU continues to be a strong medical unmet need and calls for a new drug which can comprehensively address the underlying structural and functional abnormalities through which DM impairs wound healing. There is a dire need to improve the clinical outcomes and improve the quality of life of Subjects with DFUs.

14% Galnobax®, a gel formulation for topical administration with an approved drug substance (Esmolol hydrochloride) with favorable data from the Phase 1/2 clinical study and non-clinical studies has not only been found safe, demonstrated more comprehensive ability to address the underlying structural and functional abnormalities through which DM impairs wound healing but has also demonstrated potential to be more effective in delivering better outcomes namely:²¹

- a. Complete closure in older non-healing DFUs compared to the Vehicle (75% v/s 43%)
- b. Faster complete closure compared to the Vehicle (35 days v/s 64 days)
- c. Higher area reduction over Vehicle in 12-weeks treatment (98.1% v/s 75.8%)
- d. No local reaction or risk of long term use of drug is anticipated

In addition, Galnobax® provides a tissue adherent thermo-reversible polymeric gel suitable for application on chronic wounds.²¹

Therefore, there are sufficient known and well evidenced benefits of Galnobax® for the treatment of DFU.

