3 OBJECTIVES AND ENDPOINTS

OBJECTIVES	ENDPOINTS	JUSTIFICATION FOR ENDPOINTS
Primary		

 To assess the efficacy of Galnobax® in terms of proportion of Subjects achieving Target Ulcer Closure within 12-week Treatment Phase upon application of Galnobax® plus Standard of Care as against only Standard of Care treatment, as assessed by the blinded Investigator 	
The efficacy assessment will involve Galnobax® plus Standard of Care and only Standard of Care groups
 
Efficacy endpoints:
 
Proportion of subjects achieving Target Ulcer Closure within 12-week Treatment Phase, as assessed by blinded Investigator
	Complete wound closure of a chronic, nonhealing wound is one of the most important objective and clinically meaningful wound healing endpoint
Secondary		
Efficacy	Efficacy endpoints	

 To compare Time to Target Ulcer Closure within the 12-week Treatment Phase, upon application of Galnobax® plus Standard of Care as against only Standard of Care treatment, as assessed by the blinded Investigator 	
 Time to Target Ulcer Closure during the 12-week Treatment Phase, as assessed by the blinded Investigator 	This endpoint evaluates clinically meaningful reduction in the time to Target Ulcer Closure using a time-to-event analysis (the event being first observation of complete closure)

 To compare proportion of Subjects achieving Target Ulcer Closure till End of Study upon application of Galnobax® plus Standard of Care as against only Standard of Care treatment, as assessed by the blinded Investigator 	
 Proportion of Subjects achieving Target Ulcer Closure till End of Study, as assessed by the blinded Investigator 	This endpoint is for evaluating sustained effect of the treatment post its discontinuation
Safety		

 To investigate the safety of Galnobax® treatment during the Study 	
 Proportion of Subjects with treatment emergent adverse events (TEAEs) 	This endpoint evaluates safety of Galnobax® by assessing TEAEs

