4 STUDY DESIGN

4.1 OVERALL DESIGN

This Study is a Phase 3, multicenter, randomized, double-blind, parallel-group Study designed to evaluate the safety and efficacy of Galnobax® plus SoC versus only SoC, in treating DFU in adults with diabetes mellitus (DM). In addition, Study is designed to evaluate safety of Vehicle plus SoC versus only SoC in Subjects with DFU to investigate deleterious effects of Vehicle on wound healing, if any.

For this purpose, the Subjects will be randomized in 3:3:1 ratio into one of the following groups:

- Group 1: Galnobax® 14% gel plus SoC
- Group 2: SoC only
- Group 3: Vehicle plus SoC

Total number of Subjects in the Study: This Study will have FAS Population (Efficacy Evaluable Population) of a minimum of 240 Subjects in Group 1 and Group 2 (minimum of 120 in each Group). To ensure this and assuming 20% drop out rate, the population of two groups would be maximum of 300 Subjects. In addition, for investigating the effect of vehicle on wound healing, Vehicle plus SoC group will recruit up to 50 Subjects. Thus, overall 350 Subjects will be recruited in the Study.

No. of investigational sites: This Study will be conducted at approximately 40 sites across India with competitive recruitment amongst sites.

Maximum duration of a Subject in the Study: The maximum total duration of Subject in the Study will be 25 weeks spread over three phases in following sequence:

- Screening Phase of 1-week (7 + 3 days)
- Treatment Phase of a maximum of 12-weeks (84±3 days) starting with Baseline visit
- Follow-Up Phase of 12-weeks (84±5 days). This will comprise of Closure Confirmation period of 4 weeks (28±3 days) and Observation period of 8 weeks (56±5 days).

Subject Number Assignment: The Subjects will be assigned randomization number using an interactive web-based randomization system (IWRs). Prior to randomization, Subjects will be stratified by location (plantar or non-plantar) and size ($<5\text{ cm}^2$ or $\geq 5\text{ cm}^2$) of the Target Ulcer solely for the purpose of bringing homogeneity among the three treatment Groups in proportionately. Once a randomization number has been assigned, it cannot be re-assigned to any other Subject.

Application of Treatment: Subjects in the Study will receive treatment twice daily during the 12-weeks of Treatment Phase or up to the Target Ulcer Closure, whichever is earlier. During this period, the twice daily treatment to the Subjects in all the arms of the Study will be administered

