4.2 SCIENTIFIC RATIONALE FOR STUDY DESIGN

The Study consists of about one week (7 to 10 days) of Screening period to confirm the suitability of Subject for the Study and to restrict recruitment of Subjects having healing ulcers. The Study has Treatment Phase of up to 12-weeks (84 ± 3 days) or the Target Ulcer Closure, whichever happens earlier as the Investigational Product (IP) requires 12-weeks of treatment to establish its efficacy. In view of this, if the Target Ulcer re-opens within these 84 days, the Subject will resume the treatment, up to completion of the Treatment Phase or the Target Ulcer Closure, whichever is earlier. If Target Ulcer closes prior to 12-week, then the Subject enters the 12-week Follow-Up phase immediately. The 12-week Follow-Up is required to confirm Target Ulcer closure, assess strength of closed Target Ulcer, assess progression of open wounds post Treatment Phase in terms of wound size and AEs, if any.

In this trial, Subjects will be randomized in three Groups viz, Galnobax® plus SoC, only SoC, and Vehicle plus SoC in 3:3:1 ratio. A large population is required to achieve statistically significant efficacy endpoint for wound closure, whereas relatively smaller number of Subjects are sufficient to assess non-deleterious effects of Vehicle gel. During randomization, the Subjects will be stratified based on location as well as size of the Target Ulcer to have a proportional population in the three groups. Since SoC only is the treatment of choice used in clinical setting for DFU presently, this trial uses SoC only as comparator arm to Galnobax® plus SoC treatment for efficacy analysis. The parameters of Vehicle plus SoC arm will be compared with only SoC arm to check if Vehicle has any deleterious effects on wound healing.

The FAS Population (Efficacy Evaluable Population) will include all randomized Subjects who have at least 6 weekly assessments for Target Ulcer Closure or has Target Ulcer closed earlier than 6 weeks. The efficacy analysis in this Study will use FAS Population in order to ensure that Subjects have received reasonable treatment, and are assessed for Target Ulcer Closure by blinded Investigator.

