9.4.4 SAFETY ANALYSES

Safety will be analyzed for all Subjects in ITT Population in the three groups. No formal statistical analysis will be performed.

To investigate the safety of Galnobax® vehicle for establishing non-deleterious effects of Vehicle on wound healing, number and percentage of events as well as number and percentage of Subjects with events related to local wound assessment (local pain, edema, erythema) of Target Ulcer in Vehicle plus SoC group will be tabulated and reported.

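### The vehicle objective is about wound healing, but Section 9 answers it with local pain, edema and erythema and specifies no closure estimate for the Vehicle arm

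*Combined protocol and SAP*

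**What the plan says.** **Objective.** The Synopsis and Section 3 give a safety objective on the "vehicle for establishing non-deleterious effects of Vehicle on wound healing".

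**Endpoint.** The one endpoint paired with it is "Proportion of Subjects with events related to the local wound assessment of Target Ulcer in Vehicle plus Standard of Care group".

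**Design.** Section 4.1 says the "Study is designed to evaluate safety of Vehicle plus SoC versus only SoC in Subjects with DFU". Section 4.2 says that the parameters of the Vehicle arm "will be compared with only SoC arm to check if Vehicle has any deleterious effects on wound healing". It names no parameter and no method.

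**Analysis.** Section 9.4.4 opens by saying that safety is analysed in the ITT population in the three groups, without formal statistics. Its vehicle paragraph then says that events "related to local wound assessment (local pain, edema, erythema) of Target Ulcer in Vehicle plus SoC group will be tabulated and reported".

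**Closure.** Section 3 states that "The efficacy assessment will involve Galnobax® plus Standard of Care and only Standard of Care groups". Sections 9.4.2 and 9.4.3 confine week-12 closure, time to closure and closure to End of Study to Groups 1 and 2.

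**Status of the arm.** Section 9.2 proposes no hypothesis test or statistical comparison for it and expects a reasonable estimate of safety from 50 subjects.

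**Data.** The Schedule of Activities and Section 8.1 have the Target Ulcer measured at every visit, with no arm excluded.

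**The concern.** Pain, edema and erythema are local signs, not measures of healing. Section 3 itself describes complete closure as among the most important and clinically meaningful healing endpoints, yet Section 9 asks for no closure figure in the arm whose purpose is to show that the gel base does not impair healing.

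If Section 9 is followed as written, the report could conclude that Vehicle does not harm healing without showing a healing measure for it. A vehicle that delays closure without enlarging the ulcer or raising local signs would not show in any table named there. The arm is randomised and stratified together with SoC, so a direct estimate is available from data already collected.

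**Working it through.** **1. Objective set against analysis**

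| Place | What it covers for Vehicle | Healing measure? |
|---|---|---|
| Synopsis and Section 3, objective | Non-deleterious effect on healing | Required |
| Section 4.2 | Comparison of unnamed parameters with SoC, to check healing | Promised, not specified |
| Section 9.2 | No statistical comparison | No |
| Section 9.4.1 | Categorical data summarised by treatment group | General rule; closure not named |
| Sections 9.4.2, 9.4.3 | Groups 1 and 2 only | Vehicle left out |
| Section 9.4.4, vehicle paragraph | Local pain, edema, erythema | No |
| Sections 8.2.5, 9.4.4.1 | Ulcer enlargement or worsening is an AE; TEAE tables | Worsening only |
| Section 8.2.7 | Disease progression and lack of efficacy of the IP are not AEs | Cuts across 8.2.5 |

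Section 6.2.1 counts Vehicle gel as IP, so the exclusion in 8.2.7 can apply to this arm too. A descriptive estimate would be consistent with 4.1, 4.2 and 9.2 together, but none of them specifies one.

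**2. The plan's own figures**

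Inputs from Section 9.2: 39% versus 60%, two-sided alpha 0.05, power 90%, 20% dropout. With pooled variance and mean rate 0.495:

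n = [1.96√(2×0.495×0.505) + 1.2816√(0.39×0.61 + 0.60×0.40)]² / 0.21² = 117.03, so 118 per arm.

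The plan states 120, which gives 90.7% power. 240/0.8 = 300, and 350 split 3:3:1 is 150:150:50. The figures reproduce. No calculation lies behind the 50 in the Vehicle arm.

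**3. Precision of a closure difference, Vehicle plus SoC minus SoC**

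Half-width = 1.96 × √[pV(1−pV)/nV + pS(1−pS)/nS].

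- SoC: pS = 0.39, from Section 9.2.
- Vehicle: no rate is assumed in the plan, so a range is used.
  - 0.24 is an illustrative harm case.
  - 0.39 is equality with SoC.
  - 0.43 is the only Vehicle closure rate in the documents. Section 2.2 reports "complete closure in 75% Subjects Vs 43% in Placebo group" for ulcers older than 8 weeks in the Phase 1/2 study; Section 2.3.2 calls the same comparator Vehicle.
- Numbers: 50 versus 150 (planned maxima), and 40 versus 120 (20% loss in all arms; Section 9.2 states it only for Groups 1 and 2).
- ITT variant at 50 versus 150: the 20% are counted as not closed, so each rate is multiplied by 0.8 (SoC 0.312; Vehicle 0.192, 0.312, 0.344).

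Example, pV = 0.24 at 50 versus 150: √(0.003648 + 0.001586) = 0.0723; × 1.96 = 14.2 points.

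| Vehicle closure | 50 vs 150 | 40 vs 120 | ITT 50 vs 150, 20% not closed |
|---|---|---|---|
| 24% | 14.2 | 15.9 | 13.2 |
| 39% | 15.6 | 17.5 | 14.8 |
| 43% | 15.8 | 17.7 | 15.1 |

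(Half-widths in percentage points.)

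**4. What such an interval could show**

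- Equal observed rates: the lower limit is −15.6 points (50 vs 150), −17.5 (40 vs 120) or −14.8 (ITT variant).
- Observed 24% versus 39%: −15 ± 14.2 gives −29.2 to −0.8 at 50 vs 150; −15 ± 15.9 gives −30.9 to +0.9 at 40 vs 120.
- For scale only, a test at 50 vs 150 with SoC at 39% would have 24% power for a true 10-point harm, 48% for 15 points and 76% for 20 points.

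**The case against.** The strongest reply is that the plan already covers more than the vehicle paragraph suggests.

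- **Three-group safety analysis.** The first sentence of Section 9.4.4, with the by-group rule in 9.4.1, allows local signs to be shown for all arms. This stands. A reader might infer that SoC figures for these signs are ruled out; the text does not say that. The vehicle paragraph merely names one group and needs clarifying.
- **Worsening is captured.** Section 8.2.5 makes ulcer enlargement or worsening an AE with no size threshold. Section 7.2 lists growth above 30% for two consecutive weeks as a reason for discontinuation, and 9.4.1 tabulates primary reasons. A reader might infer that deterioration under Vehicle would go unseen; these passages do not support that. They remain only a partial safeguard: 8.2.7 conflicts with 8.2.5, and an ulcer that closes late without worsening triggers neither.
- **A healing comparison is promised.** Section 4.2 does commit to one, so it would be wrong to say the protocol never intends it. The gap is that Section 9 does not deliver it.
- **The separate SAP may add closure.** It may: 9.4.1 leaves detailed methods to it, and 9.4.12 lists key variables by subject. One cannot infer that no closure figure will ever be produced. The point is that Section 9 specifies none for a stated objective.
- **Fifty subjects are too few.** They are too few for a useful test, and none is proposed. An estimate with its interval fits the aim in 9.2.

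**Conclusion.** The concern holds as a gap between the objective (with the comparison promised in Section 4.2) and the analysis in Section 9. Slower healing without worsening would appear in no table that Section 9 names, although the data to estimate it are collected in every arm.

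The added estimate would be imprecise: half-widths of about 14 to 16 points at 50 versus 150, 16 to 18 at 40 versus 120, and 13 to 15 in ITT with 20% counted as not closed. This rests on SoC closure of 39%, Vehicle closure of 24% to 43%, and equal loss in all arms. Only a large harm could be excluded; the planned drug effect is 21 points. Nothing in the documents suggests that Vehicle does impair healing, and that should not be inferred. The primary analysis is unaffected. The change should be made, but it is not a condition for the trial's main conclusion.

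**What to change.** 1. In Section 9.4.4, report the week-12 Target Ulcer Closure proportion for Vehicle plus SoC beside SoC, with the Vehicle minus SoC difference and its 95% confidence interval. Use the ITT (safety) population, label it descriptive (estimation only), and state how subjects without confirmed closure are handled.
2. Clarify there that local pain, edema and erythema are tabulated for all three arms.
3. Reconcile Sections 4.1, 4.2 and 9.2 with wording such as: no hypothesis test; the difference from SoC is estimated with a 95% CI.
4. Reconcile Sections 8.2.5 and 8.2.7 on whether ulcer worsening is recorded as an adverse event.

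Optional: speak of estimating rather than establishing in the objective, and repeat the closure estimate in the FAS.

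The cost is a few table rows and some wording, with no extra subjects or visits and no effect on the primary analysis or its alpha. The downside is a wide interval that will not support a firm statement of no harm.

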9.4.4.1 TREATMENT EMERGENT ADVERSE EVENT

Treatment emergent adverse events (TEAE) are undesirable events not present prior to medical treatment, or an already present event that worsens either in intensity or frequency following the treatment. The TEAEs, which is defined as all AEs on or after the application of first dose of IP will be summarized according to the numbers and percentages of TEAEs as well as numbers and percentages of Subjects with one or more occurrences of TEAEs during the Study. Number of Subjects with TEAEs and number of events of TEAEs will be tabulated by preferred term (PT) and system organ class (SOCL). If a Subject had more than one TEAE, event will be counted only once in SOCL and once for each PT.

Summaries of TEAEs by severity grade, relationship to Study medication, leading to death, SAEs of study, IP related TEAEs will be provided.

Also, summarization for SAE, SAEs by severity, SAEs by relationship to Study IP will be provided separately.

Listing will be provided for all Subjects who have at least one adverse event.

AEs will be coded using the MedDRA, version 20.0 or later.

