2.3 RISK/BENEFIT ASSESSMENT

2.3.1 KNOWN POTENTIAL RISKS

Phase 1/2 study of Galnobax® on 44 DFU Subjects reported the following:

- a. No deaths were reported during the study.
- b. There were 4 SAEs (arthritis bacterial, infected skin ulcer, gastroenteritis, and cellulitis) reported during the study, all in the Galnobax® 20% group and none determined by the Investigator as related to the study drug. All these SAEs were resolved during the study.
- c. There were 29 AEs of which only 2 were determined by the Investigator as related to the Study drug (TEAEs) with 1 Subject each in the Galnobax® 14% [TEAE: skin discoloration] and Galnobax® 20% [TEAE: erythema] groups. Both these events were non-serious and mild in intensity which were reversible on discontinuation of drug. None of the vital signs and Electrocardiogram (ECG) abnormalities were reported as TEAEs.
- d. Furthermore, the drug substance used in Galnobax® (Esmolol hydrochloride) is approved for intravenous application with all reported AEs being mild, transient and reported to be reversible after discontinuation of dosing in spite of systemic concentration of 868-1470 ng/mL²³ and human peak plasma concentration of 500, 1200 and 2500 ng/mL respectively at the infusion rate of 100, 250 and 500 µg/kg/min²². As against this, the clinical pharmacokinetic (PK) studies of Galnobax® conducted as part of the Phase 1/2 study demonstrated that the systemic concentration of its drug substance (Esmolol hydrochloride) through topical administration was below quantification limit (10 ng/mL) at any time during the treatment period, irrespective of wounds of different sizes and doses of Galnobax®. This low systemic absorption and localized action is also substantiated by non-clinical PK studies conducted in Lewis rats and in minipigs.²¹

The non-clinical toxicity studies of Galnobax® showed slight irritation in rabbit model which was found to be reversible and did not elicit skin sensitization in guinea pig model.

All of the above is sufficient to conclude that Galnobax® with no deaths, no SAEs related to the drug, only 2 drug related AEs which were reversible and minimal systemic absorption (way below approved tolerated concentrations) as established in Phase 1/2 study has a favorable human safety profile.²¹

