8.1 ASSESSMENTS AND PROCEDURES IN THE STUDY

The assessments and procedures in the Study are as follows:

Ankle-Brachial Index (ABI): Measurement of the ABI will be performed in a clinician's office using a blood pressure (BP) cuff and handheld Doppler device with a vascular probe (See Attachment 2). Systolic BP will be determined in both arms and both ankles. ABI will be assessed at Screening Visit V1.

Random blood glucose measurement: Random blood glucose measurement will be done at Baseline Visit V2 and all Treatment and Follow-up Visits (V3 to V18). If abnormality is observed, the Investigator may recommend pre- and post-prandial blood glucose measurement and modify medication for adequate blood sugar control. This test will be performed locally.

Assessment of study foot: Study foot will be assessed at Screening Visit V1 by Semmes Weinstein (SW) 5.07 monofilament test. Peripheral neuropathy will be assessed by using a 10 g SW 5.07-gauge monofilament to test 4 points on the foot for touch sensation (Greater toe, 1st, 3rd and 5th metatarsal head) (See Attachment 3).

Detail foot examination: Detail foot examination to assess vascular, neurological, dermatological and musculoskeletal signs and symptoms of the foot under Study will be done at Screening Visit V1, Baseline Visit V2, every 4 weeks thereafter during treatment visits (i.e. at V6, V10, and V14 or EOT) and during follow-up at V18 or EOS/FU4, whichever is earlier.

Local examination and infection status of Target Ulcer for presence of edema, warmth, erythema, pain, scaling, pus, exudates, cellulitis, callus, maceration or swelling and any signs of infection will be done at all Visits (V1 to V18).

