8.2.10 EVENTS OF SPECIAL INTEREST

Not-applicable

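### No planned table gives Target Ulcer or study-foot infection by arm, so a difference could be fragmented or diluted in the adverse-event tables

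*Combined protocol and SAP*

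**What the plan says.** **Collection.** Section 8.1 covers the local examination and infection status of the Target Ulcer; the examination for listed local findings and "any signs of infection will be done at all Visits (V1 to V18"). The Schedule of Activities records infection of non-study ulcers on a separate row. Section 8.2.3.3 makes infection of a target or non-target ulcer a reportable adverse event. Section 7.2 lists as reasons for discontinuation a Target Ulcer infection that needs topical antimicrobials, and osteomyelitis or cellulitis of the target foot.

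**Analysis.** Section 8.2.10, on events of special interest, reads "Not-applicable". Section 9.4.4.1 states: "Number of Subjects with TEAEs and number of events of TEAEs will be tabulated by preferred term (PT) and system organ class (SOCL"). It adds: "If a Subject had more than one TEAE, event will be counted only once in SOCL and once for each PT". Separate summaries of serious events and a listing are planned. The local wound tabulation in Section 9.4.4 covers pain, edema and erythema in the Vehicle group, not infection. Safety is descriptive, in all three groups.

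**Background.** Section 2.3.1 describes a Phase 1/2 study "on 44 DFU Subjects reported the following". It says: "There were 4 SAEs (arthritis bacterial, infected skin ulcer, gastroenteritis, and cellulitis) reported during the study, all in the Galnobax® 20% group", with "none determined by the Investigator as related to the study drug", and all resolved. Section 2.2 concludes that "it is proposed to investigate Galnobax® 14% in a Phase 3 Study".

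**The concern.** Infection of the treated ulcer is a safety outcome the protocol itself expects might occur, checks at each visit and, in some forms, treats as a reason to stop. The natural safety question for a gel applied to an open wound is what proportion of subjects in each arm had an infection of that ulcer or foot. The data to answer it are collected, but no planned output does so. A reader of the study report would have to assemble the answer from several preferred-term rows without double counting subjects, or read it from an organ-class total that also holds infections elsewhere in the body.

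The counting sentence adds a second difficulty. If each event is counted once per subject per term, the promised event count equals the subject count in every preferred-term row, and recurrent infection of the same ulcer disappears.

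**Working it through.** The plan states no infection rate and no figure for infection, so there is none to reproduce. The only design inputs needed are the arm sizes.

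**1. Arm sizes.** Section 9.2 gives 240 evaluable subjects and 20% drop-out: 240 / (1 − 0.20) = 300 randomized to Groups 1 and 2, or 150 each. The 3:3:1 ratio then gives 50 in the Vehicle group.

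**2. Which planned outputs could show study-foot infection?**
- *Preferred-term rows* divide it among terms such as infected ulcer, cellulitis and osteomyelitis. The target and non-target ulcers are not distinguished.
- *Organ-class row* counts each subject once, but non-target and systemic infections are included. Section 5.2 allows up to three ulcers below the knee, and entry with an infected ulcer on the other foot.
- *Serious-event tables* omit non-serious infection.
- *Discontinuation reasons by group* (Section 9.4.1) omit infections treated with systemic antibiotics in subjects who continue, which Section 6.5 allows.
- *Local wound tabulation* does not include infection.

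None isolates the outcome.

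**3. What splitting or diluting costs (illustration only).** Assumptions: study-foot infection risk doubles; 150 per arm; two-sided 0.05; either three equal, non-overlapping preferred terms, or one organ class with an independent 10% of unrelated infections in each arm. No test is planned, so power serves here only as a measure of sensitivity.

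Power = Φ[(|p1 − p2| − 1.96·SE0) / SE1], where SE0 = √(2·p̄(1 − p̄)/150), SE1 = √([p1(1 − p1) + p2(1 − p2)]/150) and p̄ is the mean of p1 and p2.

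For 10% versus 20%:
- Grouped: SE0 = √(2 × 0.15 × 0.85/150) = 0.0412; SE1 = √((0.09 + 0.16)/150) = 0.0408; (0.10 − 0.0808)/0.0408 = 0.47; power 68.1%.
- One of three terms, 3.33% versus 6.67%: SE0 = 0.0252, SE1 = 0.0251; (0.0333 − 0.0493)/0.0251 = −0.64; power 26.2%.
- Organ class: 1 − 0.90 × 0.90 = 19% versus 1 − 0.80 × 0.90 = 28%; SE0 = 0.0490, SE1 = 0.0487; (0.09 − 0.0960)/0.0487 = −0.12; power 45.1%.

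| Assumed risks | Grouped | One of three terms | Organ class |
|---|---|---|---|
| 5% vs 10% | 37.5% | 15.0% | 17.9% |
| 10% vs 20% | 68.1% | 26.2% | 45.1% |
| 15% vs 30% | 87.9% | 37.5% | 72.3% |

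**4. Precision of a grouped outcome.** At an assumed 10% in both arms:
- Galnobax versus SoC: 1.96 × √(0.09/150 + 0.09/150) = 1.96 × 0.0346 = ±6.8 points.
- Vehicle versus SoC: 1.96 × √(0.09/50 + 0.09/150) = 1.96 × 0.0490 = ±9.6 points.

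**5. Phase 1/2 count.** Infected skin ulcer and cellulitis are plainly skin or ulcer infections: 2 of 4. Counting bacterial arthritis gives 3 of 4, but nothing in the text links it to the wound. Gastroenteritis is not a wound infection.

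**The case against.** The strongest reply is that infections are not left to preferred terms. Section 9.4.4.1 tabulates by organ class too, counting each subject once. If the infection terms share one class (the documents do not say so), a per-arm proportion with any infection is already planned. Serious-event tables, listings and discontinuation reasons by group add to it. This stands: a large excess would be visible. It does not remove the gap, because no output isolates the treated ulcer or foot.

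Second, a reader might infer that Phase 1/2 left an infection signal for this trial to resolve. The documents do not support that. All four serious events were at 20%, none was judged related, all resolved, and this trial tests 14%. Nor can a useful probability be put on all four falling in one arm: arm sizes and the number of affected subjects are not given, and the arm would be singled out after seeing the data.

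Third, a reader might think that discontinuation under Section 7.2 hides infections. It does not: treated subjects stay in the safety population, and adverse events are sought until End of Study.

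Fourth, the counting sentence may be meant for subject counts only, since subjects and events are promised separately and Section 8.2.4 asks for the onset and duration of each intermittent episode. That reading is plausible, but the text does not say so.

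Finally, Section 9.4.1 defers detail to a separate SAP before database lock. Such a table could appear there; the present text does not commit to one.

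**Conclusion.** The point holds as a gap in safety reporting, not as an error in a stated figure. The plan collects Target Ulcer infection at every visit but specifies no by-arm proportion for it or for study-foot infection. The likely consequence is a fragmented or diluted comparison. To say that an excess could go wholly unseen would be too strong. Under the assumed doubling from 10% to 20%, power falls from 68% for a grouped outcome to 45% at organ-class level and 26% for a single term. Those figures rest on assumed rates, equal splitting into three terms and 10% unrelated infection; the documents supply none of these. Grouping does not make the trial decisive: at 10% the interval is still about ±6.8 points against SoC for Galnobax and ±9.6 for Vehicle. The counting rule needs clarification whichever reading was intended. Phase 1/2 is weak background, and the conclusion does not depend on it.

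**What to change.** - In Section 9.4.4.1, with a matching entry in Section 8.2.10, pre-specify one grouped outcome: Target Ulcer or study-foot infection, comprising ulcer infection, cellulitis, osteomyelitis and septic arthritis of the study foot. List the contributing terms, and use the infection-status record to identify the ulcer concerned.
- Report subjects and episodes per arm in the safety population, with descriptive risk differences and 95% confidence intervals for Galnobax versus SoC and Vehicle versus SoC.
- Summarise per-visit Target Ulcer infection status by arm.
- State that the once-only rule governs subject counts and that event counts include every episode.
- Reconcile Section 8.2.5, which makes ulcer worsening an adverse event, with Section 8.2.7, which excludes disease progression at the Investigator's discretion, since both affect which ulcer events reach the tables.

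The cost is wording in the protocol and the separate SAP, plus one or two tables from data already collected. No extra visits or subjects are needed. The intervals will be wide, especially for Vehicle, and should be presented as descriptive.
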